16.3. Endpoints

16.3.1. Primary Endpoint

- The primary endpoint is the assessment of safety and tolerability of Ad-RTS-hIL12, administered by intratumoral injection plus veledimex administered PO, as determined by the AE rate and the occurrence of DLTs analyzed specifically for each cohort.

16.3.2. Secondary Endpoints

- Determination of the recommended Phase II pediatric veledimex dose when given with intratumoral Ad-RTS-hIL-12 [REDACTED]
- Veledimex PK estimates
- The ratio of the concentration of veledimex in the brain tumor and the blood [REDACTED]
- Investigator assessment of response, including ORR and PFS
- OS

[REDACTED] [REDACTED] [REDACTED]

16.4. Analyses

16.4.1. Baseline Demographics and Characteristics

Demographic and baseline disease characteristic data will be summarized. Data to be tabulated will include at least demographic features such as sex, age, and race, as well as disease specific status and medical history.

Categorical data will be summarized using counts and percentages based on non-missing values. For continuous variables, the mean, median, standard deviation, minimum, and maximum values will be presented. Data will be summarized by dose cohort and according to the defined populations for analysis.

16.4.2. Safety Analyses

For the first veledimex dose cohorts in Arms 1 and 2 (*i.e.*, Cohorts 1 and 3, respectively), a minimum of three ESP subjects must be eligible for evaluation of safety. In addition, evaluation of any DLTs will be performed according to protocol-defined criteria. Safety variables will be tabulated and presented by arm and by dose cohort.

Safety evaluations will be based on the incidence, intensity, and type of AEs and SAEs. Clinically significant changes in the subjects' physical examinations, vital signs, ECG evaluations, and abnormal laboratory values will be captured as AEs. Safety will also be assessed based on medical history and prior/concomitant medications.

The safety evaluation period extends from the date the subject signs the ICF or assent form, as applicable, through the Initial Follow-up Period (Day 56), unless the subject discontinues from active follow-up due to one of the following reasons:

- Symptomatic deterioration also denoted symptomatic progression
- Loss to follow up
- Noncompliance with the protocol
- Other reason not listed above

Exposure to study drug(s) and reasons for discontinuation of study treatment will be tabulated. All treatment emergent- AEs (TEAEs) will be coded according to the System Organ Class and Preferred Term using the Medical Dictionary for Regulatory Activities (MedDRA). The TEAEs will be tabulated by number and percent of subjects according to relationship to the study drug(s), severity, and seriousness. A TEAE is defined as any AE that occurs during or after administration of the first dose of study drug through the evaluation period for safety defined above, regardless of relationship to study drug; or any event that is present at baseline that worsens in intensity or is subsequently considered to be drug related by the Investigator. Deaths, SAEs, and AEs resulting in study discontinuation will be listed.

After the conclusion of the safety evaluation period is triggered by a discontinuation event, the subject continues to be followed only for OS.

Laboratory parameters will be summarized by visit. Listings of vital signs and physical examination data will be listed by visit.

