Arm 1: This study has been modified to explore one veledimex dose in Arm 1: 10 mg.

Arm 2: This study is designed to explore two veledimex doses in Arm 2: 10 mg and 20 mg. Subject enrollment and veledimex dose escalation will proceed according to a standard 3+3 design. The first cohort will receive 10 mg veledimex followed by the second cohort receiving 20 mg veledimex.

Arm 1 and Arm 2 subjects may exhibit different safety and tolerability profiles. The 3+3 standard study design has been modified to independently evaluate the two arms separately.

The study arms and assigned doses will be divided into 3 cohorts as shown below:

Table 4a: ATI001-103 Cohorts

Arm	Cohort	Indication	Procedure	Assigned Veledimex Dose ^a
1	1	Resectable pediatric brain tumor	Craniotomy	10 mg
2	3 ^b	DIPG	Stereotactic	10 mg
2	4	DIPG	Stereotactic	20 mg

^a Doses are BSA-adjusted doses

^b Arm 1 Cohort 2 was removed in Protocol Amendment 2. The SRC reviewed the safety profile of Arm 1 Cohort 1 and determined it was appropriate to move forward with Arm 1, Cohort 2 and Arm 2, Cohort 1, however due to issues with enrollment of supratentorial patients, it was determined not to proceed with Cohort 2.

Note: After the completion of a phase I dose escalation cohort in Arm 2, the SRC may elect to expand that cohort by up to 30 DIPG patients, which will be considered the Phase II component of study.

Each cohort will consist of subjects \leq 21 years-of-age who meet eligibility criteria.

Each subject in each dose escalation cohort will be monitored for 28 days after Ad-RTS-hIL-12 injection before additional subjects are enrolled in the same cohort. The evaluation period for DLT is 28 days after Ad-RTS-hIL-12 injection (Day 0 to Day 28).

Determination of safety and the recommendation to expand the current dose cohort, dose escalate, or discontinue the investigation, will occur after all dosed subjects in a cohort have been evaluated for at least 28 days after Ad-RTS-hIL-12 injection, as described in Section 7.3.

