14.6. Documenting Adverse Events

All AEs, including SAEs, are to be accurately recorded on the Adverse Event page of the subject’s electronic CRF from the time the subject signs the ICF or assent form through the initial follow-up period (Day 56). AEs that are ongoing at the end of the Initial Follow-up Period and are considered drug related should be followed until resolution or no resolution is expected.

Each event will be assessed for serious criteria, severity, and causality. The date of onset, as well as the duration of the event will be recorded. In addition, treatments provided to the subject, actions taken with the study drug, and the outcome of the AE will also be noted.

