14.7. Reporting Dose-Limiting Toxicities and Serious Adverse Events

Time Frame for Reporting

All DLTs and SAEs must be reported to the Sponsor or Sponsor designee within 24 hours of awareness, regardless of initiation of new anticancer therapy, including the following:

- Any death or SAE experienced by the subject from the signing of informed consent through the initial follow-up period (Day 56), regardless of relationship to study drug.
- Any death or SAE that the Investigator becomes aware of, and believes to be study drug related, that occurs beyond Day 56.

[REDACTED]

[REDACTED]

[REDACTED]

[REDACTED]

Questions or assistance with completing forms can be directed to Ziopharm Oncology, Drug Safety and Pharmacovigilance: [REDACTED]

Additional data concerning the SAE (e.g., diagnostic test reports, hospital summaries, *etc.*) must be promptly reported (within 24 hours of receipt) to the Sponsor or Sponsor's designee, until resolution of the SAE. Should the FDA or other National Regulatory Authority require that the Sponsor submit additional data on the event, the Investigator will be asked to provide those data to the Sponsor in a timely fashion.

Information to be Provided by the Investigator

Within 24 hours of becoming aware of the SAE or subject death, the Investigator must notify the Sponsor or designee and transmit information to the Sponsor or designee. Information (initial and follow-up) should be provided on a paper SAE Report form signed and dated by the Investigator. The SAE Report form and copies of source documents with subject identifiers redacted will be transmitted by fax. A hospital discharge summary should be provided if the subject was hospitalized. A SAE report will be considered final once all relevant information has been received and reviewed by the Sponsor.

The SAE report form is provided in the Investigator study files. A DLT specific form will be used to report DLTs and is also provided in the Investigator files. Please refer to the Investigator study files for instructions on how to complete these forms. The Investigator will provide all of the following information related to the event:

- Investigator identification
- Subject identification (e.g., subject number, initials, sex, and age or date of birth)

- Information regarding study drug administration (e.g., start/stop date, dose, and frequency)
- Day of SAE or DLT occurrence documentation on SAE or DLT report forms
- Description of event

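### Protocol 16.4.2 ends the TEAE window when a subject leaves active follow-up before Day 56 for deterioration, noncompliance or any other reason, which contradicts the Day 56 AE window in Protocol Section 14 and SAP 13.1

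*Protocol*

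**What the plan says.** Protocol Section 16.4.2 starts the safety evaluation period at consent or assent and runs it "through the Initial Follow-up Period (Day 56), unless the subject discontinues from active follow-up due to one of the following reasons". Four reasons follow: "Symptomatic deterioration also denoted symptomatic progression", loss to follow-up, "Noncompliance with the protocol", and a catch-all for anything else. The section then states: "After the conclusion of the safety evaluation period is triggered by a discontinuation event, the subject continues to be followed only for OS".

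The main limb of the TEAE definition, in the same section, counts any AE from first dose "through the evaluation period for safety defined above, regardless of relationship to study drug", so it inherits the early closure. TEAEs are to be tabulated as counts and percentages of subjects. Under Section 16.3.1 the primary endpoint rests on the AE rate and on DLTs, by cohort.

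Section 14 sets a different window. Section 14.6 has all AEs recorded "from the time the subject signs the ICF or assent form through the initial follow-up period (Day 56"). Section 14.7 requires deaths and SAEs to be reported "through the initial follow-up period (Day 56), regardless of relationship to study drug". Sections 14.2 and 14.9 also run to Day 56. None of the four has an early exit.

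SAP 13.1 likewise captures all AEs through Day 56. However, it defines a TEAE by onset or worsening in the treatment period, which the schedule of procedures places at Days 0 to 14.

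The DLT window is set separately, in Section 7.1: "The evaluation period for DLT is 28 days after Ad-RTS-hIL-12 injection (Day 0 to Day 28").

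**The concern.** The protocol gives two answers to one question: is a new AE counted if it starts after a subject has left active follow-up but before Day 56? Section 14 says to record it. Section 16.4.2 says that the subject is by then followed for survival alone and that the event falls outside the TEAE window.

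The early exit is not neutral. A subject who leaves because of symptomatic deterioration leaves for a reason linked to outcome. In this population, decline may come from the disease or from treatment: Section 7.4 describes seizures, headaches and cerebral or pontine edema as common, and expects transient neurological changes in Arm 2. Section 14.5 provides a causality assessment to separate the two, but it can only be applied to events that were collected.

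The subject stays in the denominator while later new events do not reach the numerator. The AE rate, part of the primary endpoint, would then tend to be too low.

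**Working it through.** The plan states no figure that depends on this rule, so there is nothing to reproduce. The check is a comparison of the texts, followed by arithmetic for scale.

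**1. The same event under each text.** Take a new, non-serious AE that starts after a subject has left active follow-up for deterioration and before Day 56.

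- Protocol 14.2 and 14.6: recorded.
- Protocol 14.7: does not apply, because the event is not serious. Had it been serious or fatal, it would be reported.
- Protocol 16.4.2: not a TEAE under the main limb, because the safety evaluation period has closed. It may not be collected at all, because only OS is followed. The second limb (a baseline event that worsens or is later judged drug related) has no stated end date but does not cover a new-onset event.
- SAP 13.1: captured. Whether it is a TEAE depends on what the treatment period means there.

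Protocol Section 16 says the SAP will indicate deviations from the protocol's analyses. SAP 6.1 lists the changes and does not mention this one, so the SAP does not settle the conflict.

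**2. Share of the window lost.** For exit on day d, the loss is (56 − d)/56.

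- d = 14: 42/56 = 75%
- d = 28: 28/56 = 50%
- d = 42: 14/56 = 25%

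**3. Chance that a new AE is counted in that one subject.** The documents give no AE probability or time pattern. Assume probability q by Day 56 and a constant hazard. The chance of counting the AE is then 1 − (1 − q)^(d/56).

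- q = 0.30, d = 14: 1 − 0.70^0.25 = 0.085
- q = 0.30, d = 28: 1 − 0.70^0.50 = 0.163
- q = 0.30, d = 42: 1 − 0.70^0.75 = 0.235
- d = 14, q = 0.10: 0.026
- d = 14, q = 0.50: 0.159

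**4. Effect on a cohort rate.** With q = 0.30 and one subject out on Day 14, the expected observed rate is [(n − 1) × 0.30 + 0.085]/n.

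- n = 3: 0.685/3 = 22.8%
- n = 6: 1.585/6 = 26.4%
- n = 30: 8.785/30 = 29.3%

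The constant hazard is only a convenience. Dosing ends on Day 14, so drug-related events may cluster early, which would shrink the loss. Events that become more frequent as a subject declines would enlarge it. The symptom that prompts the exit is itself an AE under Section 14.2, and this arithmetic gives no credit for it.

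**The case against.** Four arguments narrow the point.

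*The trigger is narrow.* A reader might infer that deterioration itself closes the period. It does not: the subject must discontinue active follow-up for that reason. Retention is the default elsewhere. Section 8.4 asks subjects who stop drug to complete follow-up assessments and treats substantial noncompliance as a reason to stop treatment. The Table 1 footnotes require Day 28 and Day 56 MRI even with unconfirmed progression. This stands. It limits how many subjects are affected but leaves the contradiction for those who do leave.

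*Most important events are protected.* The presenting sign of progression is recorded as an AE (14.2). Deaths and SAEs are reported to Day 56 (14.7), and Section 16.4.2 lists them. Ongoing drug-related AEs are followed to resolution. This also stands. What remains is new-onset, mainly non-serious AEs between exit and Day 56, including non-serious Grade 3 events.

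*The SAP lists all AEs.* SAP 13.1 lists AEs, not only TEAEs, for the overall safety population, and SAP 6.1 prefers listings to small-sample summaries. A collected late event would therefore be visible. This stands in part: a listing is not the AE rate, and an AE that was never collected cannot be listed.

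*DLTs are separate.* A reader might infer that the rule cuts the DLT window and biases DLT rates downward. The documents do not establish that. DLTs have their own Day 0 to 28 window, Section 7.1 defers the cohort decision until all dosed subjects have been evaluated for at least 28 days, Section 14.7 requires DLT reports within 24 hours, and Section 8.5 allows some replacement. The risk arises only if survival-only follow-up stops collection before Day 28, which would also contradict Section 7.1. In that case, exit on Day 14 would leave 14 of 28 days unobserved, and the duration criteria in Section 7.4 (at least 3 days, or more than 10 days for neurological changes in Arm 2) might never be seen to be met. Section 8.5 does not cover exits for toxicity or disease progression, and the evaluable safety population does not require 28 days of observation. How such a subject counts is therefore left open.

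**Conclusion.** The contradiction is real and lies in the current text. Followed as written, Section 16.4.2 removes new-onset AEs after an early, outcome-related exit from the primary AE rate, which would tend to be understated.

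The size cannot be estimated from the documents. It depends on how many subjects leave active follow-up before Day 56, when they leave, and whether sites follow Section 14 or Section 16.4.2. The 75% and 8.5% figures describe one hypothetical subject leaving on Day 14; the second also assumes a 30% AE probability and a constant hazard. Neither measures the trial's bias. A reader might also infer a larger distortion at the higher dose, but the documents give nothing on exit rates by dose.

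DLT counts are a conditional concern only: they suffer if collection actually stops before Day 28. If sites follow Section 14 throughout, the defect reduces to which collected AEs are counted as TEAEs.

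**What to change.** Reconcile Protocol 16.4.2 with Sections 14.2, 14.6, 14.7 and 14.9 and with SAP 13.1:

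- Remove symptomatic deterioration, noncompliance and the catch-all reason from the events that end the safety evaluation period.
- Limit the survival-only sentence to the time after Day 56.
- State that AEs are collected and counted as TEAEs through Day 56 for every dosed subject, unless death, withdrawal of consent (or the other study withdrawal that Section 8.4 mandates) or actual loss to follow-up intervenes.
- In SAP 13.1, replace the reference to the treatment period with the same first-dose-to-Day-56 window.
- State how subjects with less than 28 days of observation are counted in the DLT denominator.

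The cost is protocol and SAP wording, since Section 14 already requires the data. Reported AE rates may be slightly higher and will include some disease-related events, which the existing causality assessment can separate.

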16.4.3. Tumor Response and Overall Survival Analyses

Tumor response analysis will be performed on the ESP. The Investigator assessment of ORR and PFS will be determined for each cohort according to the baseline (Day 2 \pm 24 hours) assessment, with tumor response characterized by iRANO (Okada, Weller et al. 2015) criteria for adults, pending issuance of pediatric criteria. The OS is defined as the duration of time from the first dose of study drug to the date of death or, for subjects who are still alive two years after first dose of study drug, subjects will be censored at the last follow-up contact date. A 2-sided confidence interval will be computed for the ORR. The PFS and OS will be analyzed using Kaplan-Meier methods.

16.4.4. [REDACTED], PK, and [REDACTED]

Veledimex PK parameters will be determined based on blood (plasma) levels of veledimex using [REDACTED]

[REDACTED] here possible, descriptive statistics of the PK parameters will be provided; individual subject veledimex concentrations, actual sampling times, and PK parameters will be listed.
[REDACTED]

16.4.5. Multi-Center Study

Tumor response and safety data will be presented for each dose cohort pooled over all study centers.

16.4.6. Adjustments for Covariates

No adjustments for covariates will be made.

16.4.7. Procedures for Handling Missing, Unused, and Spurious Data

No imputation of values for missing data will be performed. Standard clinical monitoring and data management practices will be used to ensure the integrity of data.

17. STUDY MANAGEMENT

17.1. Electronic Case Report Forms and Source Documentation

For each subject, electronic case report forms (eCRFs) and corresponding source records will be maintained at each clinical site. The Sponsor or designee will provide the study sites with secure access and sufficient training on the electronic data capture (EDC) application to permit site personnel to enter and/or correct information in the eCRFs for the subjects for whom they are responsible.

The eCRFs should be completed in a timely manner, and every effort should be made to have forms completed and up-to-date in anticipation of a visit by the Sponsor's monitor. Specific instructions will be provided to the site. All requested information must be entered on the eCRF in the spaces provided. If an item is not available or not applicable, it should be documented as such; do not leave a space blank.

It is the Investigator's responsibility to ensure the accuracy, completeness, clarity, and timeliness of the data reported in the subject's eCRFs. Through the EDC application, the Investigator must provide formal approval of all subject information in the eCRFs and changes to the eCRFs to endorse the final submitted data for the subjects for whom he/she is responsible. The audit trail will show the user's identification information and the date and time of any corrections.

eCRF completion may be delegated to other study personnel; however, such delegation must be documented in writing. If, for any reason, certain data are lacking to complete an individual report form, the Investigator will provide a written statement explaining the reasons for the lack of data.

The Sponsor or designee will retain the eCRF data and corresponding audit trails. A copy of the final archival eCRF in the form of a compact disk or other electronic media will be placed in the Investigator's study file.

17.2. Good Clinical Practice

The study will be conducted in accordance with ethical principles that have their origin in the Declaration of Helsinki and are consistent with International Conference on Harmonization (ICH) Good Clinical Practice (GCP) guidelines, applicable regulatory requirements, and Ziopharm policies.

17.3. Study Monitoring

After satisfactory receipt of all necessary regulatory paperwork, the Sponsor's monitor will arrange that all study material be delivered to the study site at a mutually convenient time. An initiation visit by Ziopharm and its monitoring personnel will be made. At this meeting, all personnel expected to be involved in the conduct of the study will undergo an orientation to include review of study protocol and instruction for eCRF completion and overall responsibilities, including those for drug accountability and study file maintenance.

Throughout the course of the study, the Sponsor's monitor will make frequent contact with the Investigator, which will include telephone and/or onsite visits. During these visits, eCRFs will be reviewed for completeness and adherence to protocol. As part of the data audit, it is expected that

source documents (e.g., hospital records, office records) will be made available for review by the monitor. The monitor also will perform drug accountability checks and review of the Investigator's study file to assure completeness of documentation in all respects of study conduct.

Upon study completion, the monitor will arrange for a final review of the study files, after which the file should be secured by storage for the appropriate period as specified in Section 17.5. The Investigator or appointed delegate will receive the Sponsor's representative during these onsite visits and will cooperate in providing the documents for inspection and responding to inquiries that may arise as part of this review. The Investigator will also permit inspection of the study files by authorized representatives of the regulatory authorities.

17.4. Duration of the Study

The duration of this study from the time of initiating subject screening until the completion of survival follow-up is anticipated to be approximately 48 months, including 24 months for enrollment and 24 months for follow-up.

The overall duration is expected to be up to 2 years and 28 days for an individual subject, including the following:

- Screening period of up to 28 days
- Study treatment period of up to 15 days
- Survival status through 2 years

In addition, subjects who discontinue or complete study treatment without objective evidence of disease progression should continue to be followed until confirmed disease progression per iRANO has been documented. Subjects will be followed for survival status for two years after Ad-RTS-hIL-12 injection. The active study period refers to the study period from informed consent through the Survival Follow-up Period.

